Our recent studies have shown zinc enhances the antibacterial antibody responses in toddlers (2-5 years of age) given the oral killed cholera or the ETEC vaccine. We hope that it will also have an effect of improving the immunogenicity in younger children 6-24 months of age who are given the cholera or ETEC vaccine. For this purpose we will supplement children 6 months -2 years of age with daily zinc sulfate (10 mg/day) for two weeks prior to immunization and for the duration of the study. Two doses of the oral killed vaccine will be given two weeks apart and studies continued until a week after the second dose. Thus the study will be undertaken for a period of about 5 weeks in total. A comparison group will be given the vaccine two weeks apart without any zinc supplementation.

Sample size- A total number of 300 children will be studied (75x2= 150 for ETEC vaccine related; 75x2= 150 for cholera related groups for 2 vaccines, with and without zinc).

Time frame: Within 6 month -2 years of the initiation of the study.

Overall design for the vaccine studies:

The vaccine studies will be carried out at the Mirpur field site in urban Dhaka. For both the cholera and ETEC vaccines, two doses will be given 14 days apart. The reactogenicity will be monitored for 3 days after intake of each dose of the vaccine. In the case of the children 6 months to 2 years of age, active surveillance will be carried out by the field staff in the homes by visits every day for 3 days after intake of the vaccine. Since the ETEC and cholera vaccines have generally been found to be safe at the doses being used, passive surveillance has been used in most studies in the case of both adults and children carried out so far. We are however using more precaution by carrying out active surveillance for the children.

Blood and stool samples will be collected prior to immunization and 7 days after intake of each dose of the vaccines in volumes indicated for the immunological assays (Appendix-1-7). They will not be allowed to eat or drink one hour before and after intake of the vaccine except where specified where the duration will be longer. Only when the effect of breast feeding on the immunogenicity of the cholera and ETEC vaccine will be studied the children will be withheld from breast feeding for 3 hours prior to and one hour afterwards. They can drink water during this period.

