Although the study is an open design, the clinician in the field will code the samples before sending them to the laboratory so that the laboratory personnel will be blinded when the analyses are carried out. The laboratory will only know if the samples have to be analyzed for the cholera or the ETEC vaccine immunological responses.

Samples from vaccines that will be collected at 3 time points will be tested for antibody responses. From blood PBMC will be separated for preparation of antibody in lymphocyte supernatants (ALS, Qadri et al. 2003). ALS and serum samples collected from vaccines at the preimmune (day 0) and post-vaccination days (day 7 and day 21) will be tested for antibody responses. ALS and sera from vaccinees receiving the CF-BS-ETEC vaccine or the cholera vaccine will be tested for the IgA antibody responses to different antigens including (for ETEC CFA/I, CS1,CS2,CS3,CS4,CS5, for cholera vaccine to LPS and to CTB for both). Using fecal extracts from the vaccinees at the 3 time-points, IgA antibody responses to CFA/I, V. cholerae O1 LPS and CTB will be measured. These procedures are already set-up in the laboratory of the investigators (Qadri et al. 2000,2003). Further to test the immunogenicity of the cholera vaccine we will test the vibriocidal antibody response at the 3 time points mentioned above as well as the response to LPS (O1 Ogawa and Inaba) using sera. In addition, the IgA and IgG antibody responses to rCTB will be measured in those being immunized with the cholera or the ETEC vaccine. The serum zinc level will also be assessed at the baseline in all the children since it may have an effect on the response to the intervention(s) and the vaccination.

Safety Monitoring Committee

[name] (CSD) will serve as the Chairperson of the committee. Other members include [name].(CSD), [name] (CSD) and [name] (LSD). The members are in no way involved with the project.

Safety endpoint and safety evaluation

The primary end point for evaluating safety will be defined as the occurrence of any of the following diarrhoea, vomiting or abdominal cramps of at least moderate grade. Diarrhea will be defined as three or more loose or liquid stools in any 24-h period. A measured oral or rectal temperature above 38°C will be considered a fever.

Overall laboratory tests for the project

Vaccinees:

Stools will be cultured on MacConkey agar and tested for colonization factors of ETEC by dot blot immunoassay

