The volunteers will be recruited from the urban slums in Mirpur in Dhaka for the study. The project office will be around the same area which is at present being used for other studies ongoing in ICDDR,B (projects: 98009, 99033, 2001-027,2000-027).

Clinical and field facilities:

The clinicians in the study will coordinate the clinical component of the study in the ICDDR,B hospital and in the Mirpur field site. Clinical facility needed in the study will be provided by the study physicians and other clinicians at the Clinical Research and Service Centre of the ICDDR,B hospital in Dhaka.

Laboratory facilities:

Existing laboratory facilities are adequate.

Data Analysis:

Methods to ensure data quality

All samples will be coded before reaching the laboratory and blinded until immunological analyses have been completed.

Data management; To maintain consistency the data forms will be reviewed by the investigators. This will be carried out to ensure the completeness and accuracy of the data. After editing, data will be entered in an appropriate data entry program that will be suitable for the study.

The data will be entered into a computer and a data base created. Data will be analyzed using an appropriate statistical programme, EpiInfo version 2000 or SPSS. Descriptive statistics will be generated using EpiInfo and SPSS for Windows (Version 10.00) or SigmaStat.

Statistical analysis will be carried out using appropriate parametric and non parametric tests. Overall rates of adverse reaction and seroconversion will be compared by χ^2 test with Yates correction or by the Fisher exact test. Seroconversion for the vibriocidal response will be defined as ≥ 4 fold rise in reciprocal serum vibriocidal titer from pre to post vaccination. If necessary, vibriocidal antibody titers will be transformed to logarithms to better approximate normality.

For the CF, LPS and CTB specific responses in ALS and serum samples, a ≥ 2 fold response from baseline to post vaccination will be considered a positive response. The increase in responses due to any intervention should be at least 2 fold or higher increase from that seen in the vaccinees in whom any intervention has not been carried out. We will therefore expect to see a 4 fold higher increase in the intervention group. Differences in the geometric mean titers (GMTs) of the antibody will be compared by the Mann-Whitney test or the Wilcoxon Rank Sum Test or the Student's t-test as found appropriate.

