Appendix 5c

INTERNATIONAL CENTRE FOR DIARRHOEAL DISEASE RESEARCH, BANGLADESH
Studies to enhance and improve immunogenicity of cholera and enterotoxigenic *E. coli* (ETEC) vaccines:
Post vaccination adverse event follow up form
Surveillance After Vaccination

63. Primary vaccination

64. Date
DD MM YY

65. Day 1/ Day 2/ Day 3

66. Completeness of dosing 1 = Yes 2 = No

67. Amount ingested: 1=100% 2= \geq 90% 3= $<$ 90%

LOCAL REACTION (68 - 73)

68. Abdominal pain 1= No 2=Mild 3= moderate 4=severe	69. Distension 1=No 2= moderate 3= severe
70. Vomiting 1=No 2= Yes If yes,	71. Number/day  / day
72. Diarrhoea [$>$ 3] watery or loose stool] 1=No 2= Yes If yes,	73. Number/day  / day

SYSTEMIC REACTION (74 - 81)

74. Fever (Axillary temp $>$ 37.8°C) 1= No 2= Yes	75. If yes, temperature (°C)   .  
76. Loss of appetite/ Poor feeding 1= No 2= Yes	77. Irritability 1= No 2= Yes
78. Nausea 1= No 2= Yes	79. Dizziness 1= No 2= Yes
80. Exanthema 1= No 2= Yes	81. Other 1= No 2= Yes

82. Relation to vaccine: 1 = None 2 = Possible 3 = Probable 4 = Highly probable

83. Therapy required 1= No 2= Yes

84. Outcome 1 = resolved 2 = improved 3 = unchanged 4 = worse

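### Only the laboratory is blinded: nothing keeps the staff who record reactions at home unaware of the dissolving fluid, so the between-fluid comparison of reaction rates is open to observer bias

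*Protocol*

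**What the plan says.** **Who is blinded.** Under Coding of samples, the Protocol states: "Although the study is an open design, the clinician in the field will code the samples before sending them to the laboratory". It gives the purpose as "so that the laboratory personnel will be blinded when the analyses are carried out". The Data Analysis section, under methods to ensure data quality, repeats the rule, again for samples: "All samples will be coded before reaching the laboratory and blinded until immunological analyses have been completed". No other masking is described.

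**Who records reactions.** Under Overall design for the vaccine studies, for children of 6 months to 2 years, "active surveillance will be carried out by the field staff in the homes by visits every day for 3 days after intake of the vaccine". Two doses are given, so there are two such periods per child.

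**What is recorded.** Safety endpoint and safety evaluation defines the primary safety endpoint as any of "diarrhoea, vomiting or abdominal cramps of at least moderate grade". The day 1 to 3 follow-up form (Appendix 5c) grades abdominal pain at four levels in item 68. It records vomiting and diarrhoea as yes/no with a daily number in items 70 to 73. It ends with a causality code: "82. Relation to vaccine: 1 = None 2 = Possible 3 = Probable 4 = Highly probable".

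**What is done with it.** The Data Analysis section says: "Overall rates of adverse reaction and seroconversion will be compared by" a chi-square test with Yates correction or the Fisher exact test.

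**The concern.** The masking covers the assay readings, which are the more objective outcome, and leaves out the symptom record, which is the less objective one. A child of 6-24 months cannot report cramps. The entry comes from a parent's account, the visitor's questions and the visitor's grade. A visitor who knows which fluid the child received may probe or grade differently by arm without intending to.

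The reaction rates are formally compared, so differential recording would enter a test result and could be read as a difference in tolerability between fluids. Who is masked during home visits is a rule for conduct. It has to be set before the visits take place and cannot be repaired in the analysis.

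**Working it through.** The Protocol states no figure on this point, so there is nothing to reproduce. The check is a reading of the text, followed by an illustration of size.

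**Step 1. Is any symptom assessor masked?** Both masking statements (Coding of samples; methods to ensure data quality) name samples and laboratory staff only. The home-visit paragraph, the safety endpoint section and Appendices 5c and 5d contain no masking rule. The answer is no. The Protocol does not say that the visitor knows the fluid. It calls the design open and does nothing to prevent it.

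**Step 2. Does the visitor need the assignment?** In the formulation component all three fluids are given as 20 ml (Appendix 3). The vaccine is mixed immediately before use (Vaccine, administration and allocation), and the visits come afterwards. Appendix 5c as shown has no field for fluid or group. Two of its items, 66 (completeness of dosing) and 67 (amount ingested), do need information from the dosing. Apart from those, the form can be completed without knowing the fluid.

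**Step 3. How many children?** Three arms of 102 for each vaccine: 3 × 102 = 306, and 306 + 306 = 612 of the 1140.

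**Step 4. Illustration of size.** Inputs: n = 102 per arm (Protocol). Assumed: an equal true reaction rate p of 10% or 20% in two arms, recording that adds δ to one arm only, and a two-sided 5% level. The Protocol gives no expected reaction rate.

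One rough anchor for p comes from the Background, which cites 7-8 diarrhoeal episodes per child per year. Over 2 × 3 = 6 surveillance days this is 7 × 6/365 = 0.115 to 8 × 6/365 = 0.132 episodes. Under a Poisson assumption, 1 − exp(−0.115) = 10.9% to 1 − exp(−0.132) = 12.3% of children would have at least one. Enrolment excludes children with recent diarrhoea, so the true background may be lower.

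With i and j recorded reactors in the two arms and s = i + j, the Yates statistic is

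χ² = 2n · (max{0, |i(n − j) − j(n − i)| − n})² / [n² · s · (2n − s)],

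and a difference is declared when χ² > 3.841. The probability of this is summed exactly over i ~ Bin(n, p) and j ~ Bin(n, p + δ):

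| True rate p | δ = 0 | δ = 5 points | δ = 10 points |
|---|---|---|---|
| 10% | 2.6% | 13.0% | 43.5% |
| 20% | 3.3% | 10.4% | 32.1% |

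In children, 5-10 points of 102 is about 5 to 10 extra recorded reactors in one arm. These are pairwise comparisons within one vaccine. Neither p nor δ is a finding about this study.

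**The case against.** The strongest reply is that the open design is disclosed, the study is about immunogenicity, and home visits are described as an added precaution for the children. Much of this stands, and it limits the point in several ways.

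- **Choice of fluid.** A reader might infer that biased reaction rates would distort which fluid is carried into the breast-feeding and zinc components. The documents do not support that. The aims and the formulation section frame the question as take rates and immunogenicity. The best formulation is not defined further, and no passage makes reactions a selection criterion.
- **Prior expectation.** A reader might infer that the investigators expect CeraVax to be better tolerated. The Background says only that a less hypertonic buffer may be better and does not tie this to reactions. The vomiting problem is documented for the ETEC vaccine at higher doses, not for the cholera vaccine.
- **How subjective the endpoint is.** Diarrhoea is a stool count, and vomiting is yes/no with a number. Irritability and poor feeding on Appendix 5c are yes/no items outside the primary safety endpoint. The soft component is cramps.
- **Who judges causality.** A reader might infer that field staff do. Appendix 5c does not say who completes item 82, and the adverse event form in Appendix 5d carries an investigator's signature. No passage says that this assessor is blind either.
- **Existing codes.** The letters A, B and C in the formulation section are a list within a sentence, not coded product, so masking is not already partly in place.
- **Breast-feeding component.** A reader might extend the remedy to these 228 children. The mother carries out the feeding assignment and is also the informant, so masking the visitor would achieve little.
- **Fluid component.** The bicarbonate buffer is raspberry flavoured and one arm is water, so parents may notice or mention the taste.

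What the reply does not answer is that a planned test of reaction rates rests on records taken with no assessor masking, in a component where the visitor has no need of the assignment.

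**Conclusion.** The point holds as a design weakness in the safety comparison between dissolving fluids. It is not a contradiction in the Protocol, and it does not touch the immunogenicity results. It concerns 612 children, 102 per arm for each vaccine.

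The size of any bias is unknown. Under the assumed rates in the table, false differences between two fluids rise from about 3% of trials to 10-13% with a 5-point recording difference, and to 32-44% with a 10-point one. These figures show sensitivity, not expected error. The conclusion rests on two things: the absence of any masking rule for symptom recording, which is a matter of text, and the judgement that the fluid can be withheld from home visitors at little cost. It is a modest improvement worth making before dosing starts.

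**What to change.** Extend the rule under Coding of samples to safety data in the formulation component:

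1. The fluid assignment is held by the staff who mix and give the dose. Home visitors complete Appendix 5c from the study number only.
2. Items 66 and 67 are recorded at dosing on the vaccination form (Appendix 5b), so that Appendix 5c needs nothing from the dosing session.
3. Whoever assigns relation to vaccine (item 82) does so before learning the fluid.
4. For the breast-feeding and zinc components, the Protocol states plainly that safety assessment is open.

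The cost is some rostering of existing staff, so that a child's visitor is not the person who gave the dose, and a minor change to two forms. The Protocol shows no staffing figures, so the rostering should be checked locally. No dose, schedule or sample size changes. Masking will be partial because parents may mention the taste; the change reduces observer bias and does not remove it.

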The different components of the vaccine studies are planned and will initiate with the cholera vaccine followed by the ETEC vaccine as follows:

Sample size: The sample size has been calculated in the different interventions, using a one sided hypothesis and confidence of approximately 95%, a minimum detectable difference in mean (MDD) of 50% improvement over baseline, and with 15% for dropout adjustment.

As the whole cell cholera vaccine with standard buffer in subjects aged 2-5 years of age 36% respond with vibriocidal antibodies (Albert et al. 2003, Qadri et al.2004) the sample size of each group in the two buffer components and in the formulation in water will be 102. As our earlier work on ETEC vaccine in Bangladesh we have found on average 55% percent of children in the 6 months to 2 years of age respond with CF specific antibodies (Qadri et al. in manuscript), the sample size of the each group of the breast feeding component will be 57; Using the results obtained on zinc supplementation on the whole cell cholera vaccine in subjects aged 2-5 years of age (Albert et al. 2003, Qadri et al.2004), 36% respond with vibriocidal antibodies before and a 66% responder frequency is seen after the intervention, the sample size of each group on the zinc supplementation component will be 75.

1. The optimum buffer for formulation of the vaccines in children

We would like to evaluate the suitability of the buffer which will be used to formulate the cholera or ETEC vaccine for use in young children. In addition we will also determine if the vaccines can be used without any buffer that is in water in these children. At present we use about 400 mg of the bicarbonate buffer for formulation of the ETEC vaccine for the young children. We plan to evaluate if this amount can be omitted with retained immunogenicity of the vaccines.

We would also like to compare the immunogenicity of the ETEC and/or cholera vaccine after formulation in two different buffers in children. We will formulate the cholera and/or ETEC vaccine in CeraVacx which contains rice syrup solids, sodium bicarbonate and citric acid (Sack DA et al. 1997). Finally we will study the response in a group of children who will receive the vaccine, which has not been formulated in any buffer. The results of these studies will be used to formulate the cholera and ETEC vaccine in the most appropriate dissolving liquid.

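### The Yates-corrected chi-square or Fisher exact test fixed for seroconversion is valid but more conservative than these group sizes need, costing about 2 to 5 power points at the protocol's own sizing rates (one-sided)

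*Protocol*

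**What the plan says.** The Data Analysis section of the protocol puts safety and response rates under one rule: "Overall rates of adverse reaction and seroconversion will be compared by" chi-square "with Yates correction or by the Fisher exact test". It gives no criterion for choosing between the two tests and no sidedness. The same section defines seroconversion only for the vibriocidal titre (at least a 4-fold rise). For CF, LPS and CTB antibodies it calls a rise of at least 2-fold a positive response.

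The sample size paragraph under Research Design and Methods sizes the groups on responder rates, "using a one sided hypothesis and confidence of approximately 95" percent, with "a minimum detectable difference in mean (MDD) of 50% improvement over baseline" and "with 15% for dropout adjustment". The inputs by component are:

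- Formulation: "in subjects aged 2-5 years of age 36% respond with vibriocidal antibodies", and "the sample size of each group in the two buffer components and in the formulation in water will be 102".
- Breast-feeding: "55% percent of children in the 6 months to 2 years of age respond with CF specific antibodies", with 57 per group.
- Zinc: 36% versus 66% vibriocidal responders, with 75 per group.

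No power and no test are named for the sizing.

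**The concern.** Yates' correction and Fisher's test protect against a poor normal approximation in sparse tables. That is sensible for rare adverse reactions. Here the same sentence carries the protection over to a response expected in a third or more of the children, in groups large enough for the approximation to work. The test then rejects less often than its nominal level allows, and power is lost on the kind of endpoint used to size the groups. This matters most for formulation, the component with the lowest power at its sizing rates, because the fluid chosen there is carried into the breast-feeding and zinc studies.

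**Working it through.** **Inputs.** Planned group sizes are 102, 57 and 75. Evaluable sizes after 15% dropout are 102 × 0.85 = 86.7, 57 × 0.85 = 48.5 and 75 × 0.85 = 63.8, taken as 87, 48 and 64. A 50% relative improvement gives 36% × 1.5 = 54% and 55% × 1.5 = 82.5%. For zinc the stated pair is 36% versus 66%.

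**The protocol's own figures.** No power is stated, so the group sizes can only be inverted. With the usual uncorrected one-sided formula, z(power) = [δ√n − 1.645√(2p̄q̄)] / √(p1q1 + p2q2):

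- Formulation: (0.18 × √87 − 1.645 × 0.704) / 0.692 = 0.75, about 77%.
- Breast-feeding: (0.275 × √48 − 1.645 × 0.656) / 0.626 = 1.32, about 91%.
- Zinc: (0.30 × √64 − 1.645 × 0.707) / 0.674 = 1.83, about 97%.

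No single power reproduces all three sizes.

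**Expected counts.** The smallest is for breast-feeding non-responders: the pooled rate is (55% + 82.5%) / 2 = 68.75%, so 48 × 31.25% = 15. Neither correction is needed on the usual rule of 5.

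**What the correction does.** With a/b and c/d the responders/non-responders in the two arms, n children in each and N = 2n, write R for (a+b)(c+d)(a+c)(b+d).

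- N-1 chi-square: (N−1)(ad − bc)² / R.
- Yates: N(|ad − bc| − N/2)² / R.

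With equal arms, subtracting N/2 takes one child off the observed difference, that is 1/n: 1/87 = 1.1, 1/64 = 1.6 and 1/48 = 2.1 percentage points.

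**True level.** Exact enumeration over two binomials with equal rates, 48 to 102 per arm, common rate 20% to 80%, nominal 5%:

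- Yates: 2.9% to 4.1% one-sided, 2.7% to 4.2% two-sided.
- N-1: at most 5.6% one-sided and 5.8% two-sided. At rates outside 20% to 80% its one-sided level can reach about 6.2%.

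**Power.** Exact enumeration, counting rejections in the favourable direction:

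| Component (evaluable n per arm) | Rates | One-sided, Yates / N-1 | Loss | Two-sided, Yates / N-1 | Loss |
|---|---|---|---|---|---|
| Formulation (87) | 36% vs 54% | 74.1 / 78.8 | 4.7 | 63.3 / 68.9 | 5.6 |
| Breast-feeding (48) | 55% vs 82.5% | 87.0 / 91.0 | 4.0 | 78.5 / 84.0 | 5.5 |
| Zinc (64) | 36% vs 66% | 94.5 / 96.3 | 1.8 | 89.6 / 92.4 | 2.8 |

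One-sided, Fisher gives the same power as Yates in all three rows. With no dropout (102, 57, 75 per arm) the one-sided losses are 3.8, 2.5 and 1.0 points.

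**Sensitivity to the rates.** If 36% versus 54% is applied to the breast-feeding cholera groups (48 per arm), Yates versus N-1 is 46.6% versus 54.2% one-sided (7.6 points) and 35.1% versus 43.1% two-sided (8.0). Applied to the zinc groups (64 per arm), it is 57.7% versus 64.5% one-sided (6.8) and 45.5% versus 52.2% two-sided (6.7).

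**Holding the level strictly.** Boschloo's exact unconditional test stays below 5%. Against Fisher, one-sided, it gives 75.9% versus 74.1%, 90.6% versus 87.0% and 96.3% versus 94.5% in the three sizing scenarios. Over both sidednesses and both full and evaluable sizes, its gain at the sizing rates is about 0.1 to 3.6 points.

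**The case against.** Yates and Fisher are standard and keep the type I error below 5%. The sizing paragraph names neither a test nor a power, so nothing is contradicted; a test running at 3% to 4% still satisfies a 95% confidence statement. With three formulation arms and many antigens and sample types, a sponsor may prefer to err on the strict side. Titres are also compared separately by rank or t-tests, so the immunogenicity conclusions do not rest on this test alone. All of this stands, and it is why the point is minor.

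Three stronger readings are tempting and not supported.

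- A reader might infer a loss of up to 8 points across the trial. Losses of about 7 to 8 points arise only when 36% versus 54% is applied to the breast-feeding cholera groups or the zinc groups. The protocol does not size the breast-feeding component on that pair, and for zinc it states 36% versus 66%.
- A reader might infer that the correction buys nothing. It buys guaranteed level control, which the N-1 test does not give.
- A reader might infer that every comparison is thinly powered. At the sizing rates, one-sided, Yates still has 87% power for breast-feeding and 94.5% for zinc.

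One further limit applies. Because seroconversion is defined only for vibriocidal titres, the sentence does not clearly govern CF responders, on which the breast-feeding component was sized.

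**Conclusion.** The point holds as a minor matter of efficiency, not as an error of validity or a contradiction. For common responses at these group sizes the planned test runs at 2.7% to 4.2% instead of 5%. At the sizing rates after dropout it gives up 4.7, 4.0 and 1.8 power points one-sided, or 5.6, 5.5 and 2.8 two-sided. In the formulation component, two-sided, Yates needs about 100 evaluable children per arm to match the N-1 test with 87.

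This rests on three assumptions: 85% of children are evaluable; the planning rates hold at 6 to 24 months, although the 36% comes from children aged 2 to 5 years; and the rule for seroconversion is also used for CF responders.

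**What to change.** In Data Analysis, separate the two uses. Compare seroconversion and the other responder rates with the uncorrected (N-1) Pearson chi-square, or the equivalent score test with its confidence interval for the difference, at the sidedness used for the sizing. Keep the Fisher exact test for adverse-event tables with any expected count below 5. State explicitly that the rule for responder rates covers both the 4-fold vibriocidal and the 2-fold CF, LPS and CTB definitions.

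The cost is one line of analysis text; no extra child or sample is needed. The downside is that the true level can reach about 5.8% at response rates between 20% and 80%, and slightly more one-sided at extreme rates. If that is unacceptable, name Boschloo's test instead: it holds 5% and still recovers part of the loss.

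### Geometric mean titres are to be compared by unadjusted rank or t tests, although a day-0 titre is planned for every child; a baseline-adjusted log-titre model would be more precise

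*Protocol*

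**What the plan says.** The Data Analysis section of the protocol sets the method for titres: "Differences in the geometric mean titers (GMTs) of the antibody will be compared by the Mann-Whitney test or the Wilcoxon Rank Sum Test". A third option then follows in the same sentence, "or the Student's t-test as found appropriate". It names no covariate. It also allows that, if necessary, "vibriocidal antibody titers will be transformed to logarithms to better approximate normality".

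Baseline blood is planned for everyone. The section on sample collection and laboratory analysis states: "ALS and serum samples collected from vaccines at the preimmune (day 0) and post-vaccination days (day 7 and day 21) will be tested for antibody". Appendix 1 counts 1140 × 3 = 3420 blood samples, on days 0, 7 and 21. Age in months is recorded on the screening form (Appendix 5a).

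Day 0 does enter the responder endpoints. The threshold for vibriocidal seroconversion is 4, measured as the "fold rise in reciprocal serum vibriocidal titer from pre to post vaccination". For the CF, LPS and CTB antigens the threshold is 2, and a "fold response from baseline to post vaccination will be considered a positive response" when it reaches that value.

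In the zinc component, supplementation starts before the first vaccine dose and therefore before the day-0 sample. The section on vaccine administration and allocation and Appendix 7 give 10 days; the section on the effect of zinc gives two weeks. These passages need to be reconciled, but the order of events is the same on either reading.

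**The concern.** A child's titre before vaccination is an obvious candidate to explain part of the variation in titre afterwards. The protocol itself describes ETEC incidence as falling with age and reads this as acquired immunity. It also excludes culture-positive children because infection would interfere with judging the response. Comparing post-dose titres without the day-0 value leaves that variation in the error term and leaves any chance difference in starting titre in the estimate.

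Two features add to this. Mann-Whitney and Wilcoxon rank sum are the same test, so the real choice is between a rank test and a t-test, and it is left open. The rank test gives no GMT ratio, whereas the Data Analysis section states its target effect as a ratio: an increase at least two-fold that seen without the intervention. An estimate with a confidence interval speaks to that target; a rank-test p-value does not.

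At stake are the width of the interval around each GMT comparison and protection against baseline imbalance. The validity of the test is not at stake.

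**Working it through.** **Plan's own figure.** There is none to reproduce. The protocol gives no titre standard deviation, no day-0/post-dose correlation, and no power or sample size for a GMT comparison. The group sizes (102, 57 and 75) are presented as coming from responder percentages, "using a one sided hypothesis and confidence of approximately 95" per cent. They serve here only as counts.

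**Inputs.**
- Group sizes after 15% dropout, rounded down: formulation 102 × 0.85 = 86.7, so 86; breast-feeding 57 × 0.85 = 48.45, so 48.
- r, the correlation of log day-0 with log post-dose titre: assumed, 0 to 0.7.
- Equal spread of log titre at both times, a linear relation, and groups comparable at baseline on average: assumed.

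**Formulas, relative to comparing post-dose log titres alone.**
- Variance with day-0 adjustment: 1 − r².
- Confidence-interval width on the log scale: √(1 − r²).
- Variance of a plain change score (post minus day 0): 2(1 − r).

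| r | adjusted variance | reduction | relative CI width | change-score variance |
|---|---|---|---|---|
| 0.1 | 0.99 | 1% | 0.995 | 1.8 |
| 0.3 | 0.91 | 9% | 0.954 | 1.4 |
| 0.5 | 0.75 | 25% | 0.866 | 1.0 |
| 0.7 | 0.51 | 49% | 0.714 | 0.6 |

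**Power.** Take the effect that gives the unadjusted t-test 80% power at two-sided 0.05: 0.427 SD with 86 per group, 0.572 SD with 48. Simulated power, from 2000 runs per setting with normal log titres:

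| n per group | r | t-test | rank test | change score | adjusted |
|---|---|---|---|---|---|
| 86 | 0 | 0.793 | 0.778 | 0.501 | 0.788 |
| 86 | 0.3 | 0.808 | 0.784 | 0.654 | 0.839 |
| 86 | 0.5 | 0.804 | 0.784 | 0.797 | 0.892 |
| 86 | 0.7 | 0.790 | 0.776 | 0.946 | 0.972 |
| 48 | 0 | 0.786 | 0.768 | 0.518 | 0.781 |
| 48 | 0.3 | 0.790 | 0.776 | 0.652 | 0.826 |
| 48 | 0.5 | 0.796 | 0.780 | 0.780 | 0.893 |
| 48 | 0.7 | 0.790 | 0.773 | 0.944 | 0.970 |

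The simulation error near 0.80 is √(0.8 × 0.2 / 2000) = 0.009, so the difference of 0.005 at r = 0 is negligible. At one-sided 0.05, for an effect with 80% power unadjusted, the formula gives adjusted power of 0.803, 0.832, 0.890 and 0.967 at r = 0.1, 0.3, 0.5 and 0.7. The pattern is the same.

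**Reading.** The adjusted model gains whenever r is above zero and loses almost nothing otherwise. The change score is worse than ignoring baseline when r is below 0.5.

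**Zinc.** The order of events is zinc start, then day-0 sample, then first dose. The day-0 titre is therefore taken after the intervention has begun. If zinc altered it, adjustment could remove part of the effect being sought. In the breast-feeding component, withholding starts only hours before the dose, which I judge too short to move a serum titre.

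**The case against.** The strongest reply is that this is a preference about efficiency. Two-sample tests on titres are valid, the choice of covariates is often left to a statistical analysis plan, and one that is not shown might add them. The validity point stands. The rest does not remove the finding: the protocol names a method for the GMT comparison, and a better one is available from data it already plans to collect.

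Four further objections stand and set the limits.

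- A reader might infer that the plan ignores day 0 altogether. It does not: both responder definitions are built on it. The protocol also does not say whether GMTs are compared at day 7, at day 21 or as rises.
- A reader might infer that the group sizes should change. They rest on responder percentages, to which the 1 − r² gain does not apply.
- The correlation is unknown. If many of these young children have day-0 titres at the assay floor, r could be small and the gain close to nil.
- A t-test on log titres does yield a GMT ratio with an interval, so the lack of an effect size applies only to the rank test.

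Age is partly handled in the breast-feeding component, where controls are age matched. That is a reason to carry age into the analysis rather than to leave it out.

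**Conclusion.** The point holds as a worthwhile improvement limited to the GMT comparisons. The named tests are not wrong, but they leave out a baseline measurement planned for all 1140 children. The gain is a variance reduction of r squared: from 1% at r = 0.1 to 49% at r = 0.7, and none at r = 0. It rests on an assumed r, on roughly linear and equally spread log titres, and on groups comparable at baseline. The added value of age as a covariate cannot be sized from the protocol.

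Three stronger readings are not supported.

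- Day-0 adjustment is not a free gain in every component, because in the zinc component the day-0 sample follows the start of supplementation.
- The argument does not extend to an adjusted logistic model for seroconversion. That endpoint already uses day 0, no figure supports a gain, and an adjusted odds ratio is a different quantity from the comparison of rates that is planned.
- Adjustment would reduce the effect of baseline imbalance but would not replace random allocation. The protocol describes no randomisation procedure (a random-number field appears only on the adverse event form), and that is a separate matter.

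**What to change.** For the formulation and breast-feeding components, state as the main GMT analysis a linear regression of log post-dose titre, at a named day, on group with log day-0 titre and age as covariates. In the formulation component, group is a three-level factor. Report the adjusted GMT ratio with 95% CI. Keep one rank test, named once, as a sensitivity analysis, and remove the choice of test as found appropriate. Do not substitute a plain change score.

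For the zinc component, use the same model with age but without day-0 titre. Add day-0 adjustment as a sensitivity analysis, stating that the sample was taken after supplementation began.

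Leave the responder analyses and group sizes unchanged on this account. The cost is a few sentences in the Data Analysis section, settled before unblinded titres are seen. No extra samples, visits or assays are needed, and the software already listed can fit the model.
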